Yale University

Institutional Review Board [name] [contact] [contact]

http://info.med.yale.edu/hic

To:	[name].
From:	Yale Institutional Review Board
Date:	12/21/2016
Committee Action:	Exemption Granted
IRB Action Date:	12/21/2016
IRB Protocol #:	1612018709
Study Title:	Fluid Administration with LifeFlow vs Push/Pull.

Educational Research Conducted in Educational Settings. Research conducted in established or commonly accepted educational settings, involving normal educational practices, such as:i) research on regular and special education instructional strategies, orii) research on the effectiveness of, or the comparison among instructional techniques, curricula, or classroom management methods

Exempt studies do not require annual IRB review. Modifications to exempt research do not need a formal IRB review unless the proposed revision affects the exempt status of the protocol. Such changes may include, but are not limited to, addition of collection of identifiers when the original protocol included anonymous data only, addition of children or prisoners as study subjects, or addition of procedures that could potentially increase risk to subjects. See the Exemption Guidance (100 GD9) for more information and examples.

Whenever an exempt protocol is modified (regardless of the type of change), updated versions of all research documents affected by the change must be sent to the IRB Office for the file. Revisions to the documents must be tracked. Changes that do not require IRB review will not be acknowledged formally.

Investigators are also required to promptly report any unanticipated problems or complaints to the IRB.

Review Comments:

• EXEMPTION 45 CFR 46.101(b)(1) This research is exempt from IRB review under federal regulation 45 CFR 46.101(b)(1). This part of the regulations covers research conducted in established or commonly accepted educational settings, involving normal educational practices such as (i) research on special education instructional strategies, or (ii) research on effectiveness of or the comparison among instructional techniques, curricula, or classroom management methods.

LifeFlow Protocol:

Training:

- Participants are randomized to the device.
- A 5-minute training video is viewed on how to use the device that participants are randomized to.
- Participants are given the device, a 1L NS bag, tubing and a 22g IV. They will demonstrate ability to set up the device and fill an empty container with fluid.
- For Lifeflow:
 - Box opened, 2 pieces of tubing removed from box.
 - Blue caps taken off and 2 pieces of tubing connected
 - 1L bag spiked and connected to tubing
 - o Device unlocked, opened, and tubing inserted with plunger properly placed
 - Device pointed upward so air rises while device is pumped until primed and air removed from line.
 - Distal tubing connected to IV and participant pumps water through.
 - Participants reminded to change 1L bag when about 2cm fluid remain.
 - Line is changed from first 1L bag to second and device continues to be used.
- For Push/Pull:
 - Tubing, 3-way stopcock, 20cc syringe and 22g IV provided in an equipment box
 - Participants spike bag, connect tubing, and use syringe/stopcock to prime line.
 - Practice changing position of stopcock for fluid to flow through IV
 - Line is changed from first 1L bag to second and device continues to be used
- For Pressure Bag:
 - Tubing, sleeve, and 20 cc syringe provided in an equipment box
 - 1L bag placed in sleeve, spiked and tubing connected to IV.
 - Sleeve pressurized to 300mmHg

Set up:

- 10 kg child with a 22-gauge IV catheter x 2, device and appropriate tubing
- The distal end of the catheter was secured in an unobstructed manner within conduit tubing leading to a graduated cylinder.
- The graduated cylinder, used to collect and measure fluid kept hidden from the view of participants.
- The proximal end of the intravenous catheter was connected via a catheter extension set to the appropriate technique-dependent setup.
- Cameras set up on graduated cylinder and overall resuscitation.

Trial:

- Vitals given to participants indicating septic shock
- Algorithm available indicating 20cc/kg boluses x 3: *Clinical practice parameters for hemodynamic support of pediatric and neonatal septic shock: 2007 update from the American College of Critical Care Medicine. Crit Care Med 2009; 37:666.*
- Heart rate and blood pressure slightly improve after each subsequent bolus
- Participants prompted if necessary to continue giving fluids
- Simulation ends after 15 min, expect to also give antipyretics (Tylenol), can obtain labs and should give antibiotics
 - CHARGE NURSE BRINGS IN ANTIBIOTIC AT TIME= 8 MINUTES
 - Participants timed on setup, infusion of each bolus, total time for 3 boluses
 - Clock during simulation, verify with video
 - Compare rate of fluid administration between first, second and third boluses
- Participants will be given a follow up questionnaire regarding secondary outcomes.
 - Participants' ability to accurately administer the requested volume (60 ml/kg or 1200ml) to the simulated patient
 - Level of self-reported fatigue

ADDITIONAL SET UP—monitor, fluid pumps, simulated Tylenol and other meds, zofran Ceftriaxone and Tylenol/Zofran will arrive from pharmacy, printed copy of labs

PRESSORS and other meds will be "being prepared" and brought into the room

Introduction script:

- Begin the session with an introduction to the project and you/the parent.
- Have participant introduce themselves.
- State your basic assumption: we believe that as a participant you are intelligent, well trained, want to do your best and want to improve.
- Cardinal rule of simulation: What happens in sim stays in sim. Please do not discuss the performance of your peers or these cases outside of this session.
- Use the saying, "What happens in Vegas, stays in Vegas." In other words, what happens in Sim stays in sim. Remind participants that this is a learning environment and that they will not be judged. Rather is a test of different devices/equipment.
- Reiterate that the participants can use all the tools including computer programs, apps, and code books.
- Review the format of the day. Simulation begins with a "patch" from charge nurse who is bringing patient back. The participants will have 60 seconds to formulate their team before the actual simulation begins. The simulation will begin. It ends when the moderator says, "curtain down."
- A debriefing of the session will occur and be recorded in the room lasting about 10 minutes.
- Orient them to the mannequin. Walk them from head to toe on what the Megacode kid can and cannot do and what is expected of them. Mention the importance of "suspending disbelief." The simulator has limitations but the more the participants put into the scenario and caring for the fake child, the more that will be gained. We mention a "Disney World" story where an older sibling points out all the fake things in the amusement park to the younger sibling. But if you believe and use your imagination, the more enjoyment and the more realism will occur.
- Introduce the participants to the medication tray. Review what is expected of the participants(to order, calculate, draw-up, and administer medications as they would with a real patient).
- Discuss that they are expected to DO, not just SAY what they want. For example, if they want 20cc/kg bolus, a team member needs to place and IV or IO, get the fluid, spike the bag, hook it up to the patient, an administer the fluid. All interventions happen in real-time.

Introduce them to parent actor/character- inform them that this person will give information and at times ask questions (plus can respond to questions at any time)

• You will be videotaped during this session. These videos will be used for research purposes and not for work related evaluations. They will be secured in a safe location and will not be shared outside of this research project.

ORIENTATION TO EQUIPMENT:

- Please hook monitors to the patient when you want to obtain vital signs (SHOW ATTACHMENT OF MONITORS and have data come up on monitor).
- You can press the screen to obtain a blood pressure (SHOW THIS)
- All supplies for case are in this room.
- IVs are in place x 2 (placed at triage)
- Fluid and medication should
- be infused and medications pushed when access is obtained.
- Draw up actual volumes of medications as you would in a real patient. (SHOW HOW IV ACCESS WILL WORK and PUSH
- MEDS)
- The medications are provided in these containers. Please note that they are in alphabetical order. We encourage you to verbalize your orders and use closed loop communication during the cases. If you are looking for a medication not in the container please announce that you are ordering from pharmacy and we will provide.

Case- Hypovolemia/Sepsis

Facilitator states case lead in: *EMS brought in a 1-year-old female patient with vomiting, fevers, tachycardia, and ill appearance. She has not had any urine output in 20 hours. Patient is at triage and will be brought back to the resuscitation bay in one minute*

(Start with patient covered with a sheet and STATE patient has arrived at 1 minute and then remove the sheet)

Give 60 seconds to organize themselves, remove sheet from baby and announce: "the patient has arrived".

Start the simulator scenario running, state: patient arrived/begin simulation at sixty seconds

When they are performing initial exam state these findings as team assesses the patient:

Patient is sleepy with minimal movementsILL APPEARING, MOTTLED COLOR, GRUNTING, HOT TO TOUCH CENTRALLY
HEENT: Dry lips and mouth, PERRL, tm's normal, sunken eyes

RESP: right sided crackles consistent with pneumonia
CV: tachycardic, cap refill 4 seconds
ABD: soft, non-distended, no HSM

Skin: tenting turgor, no petechiae or purpura
EXT: warm, no signs of trauma, no rashes

Vital signs should be activated on simulator software AFTER the monitor is attached (do not show up if not attached)

VITALS: T: 103 RR: 35 HR: 160 BP:80/35 O2:96% -- minimal crying but coughing and vomiting

WILL TREND OVER 5 MINUTES to RR: 45, HR: 185, BP: 70/30

TREND OVER LAST 10 MINUTES—patient starts with more crying and coughing sounds RR: 30, HR: 140, BP: 85/45

CASE ENDS WITH SIGN OUT TO PICU @ 15 minutes from start

Information provided by parent:

IMMEDIATELY STATE: RACHEL is a healthy girl, she was sick for a few days and has been seen by her doctor two times, her brother has a cough and runny nose

- She had a fever and was seen yesterday by PMD who diagnosed with an otitis media and started amoxicillin and Zofran
- Hard to wake up today, tried to let her sleep it off but she napped for over 8 hours and cannot get her up to take her medicine.
- Drinking less today. Vomited two times. Soaked through her sheets in sweat

THROUGHOUT CASE ASK FOR UPDATES EVERY FEW MINUTE IF NOT PROVIDED BY TEAM, expect people to inform you of what is going on, you can ask for updates. You will be confused and frustrated.

AT THREE MINUTES STATE: "why is she so sleepy, what is going on, are you helping her" *AT FIVE MINUTES STATE: Is she going to be OK? Her color looks awful AT EIGHT MINUTESS TATE: I need to call her dad- what do I tell him? AT ELEVEN MINUTE: MAKE HERE VOMIT SOUND, parent asks to give her something to stop vomiting AT FOURTEEN MINUTES STATE: Ask* what does those numbers on the monitor mean- is she getting better.

Parent responds to questions when asked by the medical team:

(S)How long has she been ill? Mom: She has had a fever for two days, as high as 103. She has vomited 10 times today and once yesterday.

(A)Does she have any allergies? Mom: None that I know of.

(M)Does she take any medicines? Mom: Not regularly- she had Tylenol for her fever, and yesterday at the pediatrician's office, he gave her Amoxicillin/Zofran.

(P)When she was born, were there any difficulties? Mom: She was near term, 39 weeks, and it was a normal delivery. Does she have any past medical history? Mom She has been perfectly healthy and is up to date with her shots

(L)When was the last time she ate? Mom:. She is having trouble drinking today and not keeping anything down.

(E) What was she doing right before you brought her to the ED? Mom: She was really hard to wake up from her nap and she is breathing really heavy. I got really scared and we live close, so I rushed her right over here. Has she been using bathroom? Mom: no

RESPONSES TO QUESTIONS IF ASKED BY FACILITATOR

PHASE 1 Anytime after first fluid bolus:

What is her work of breathing? Facilitator: She is still grunting and flaring What is her capillary refill? Facilitator: still prolonged at 4 sec What is her mental status? Facilitator: She is sleepy What is her general appearance, color, temperature? Facilitator: She is less grey but she is still very cool in her extremities

PHASE 2 After second fluid bolus:

What is her work of breathing? Not terrible What is her cap refill? Facilitator: *Her capillary refill is better. now 3 seconds* What is her mental status (if not intubated)? Facilitator: *She is starting to respond some more* What is her general appearance, color, temperature? Facilitator: *She has more color now and she is less mottled.*

PHSE 3 After third fluid bolus or vasoactive medications are initiated:

What is her work of breathing? **improved** What is her capi refill? **Facilitator**: *Her capillary refill is much better at 2 seconds* What is her mental status (if not intubated)? **improved** What is her general appearance, color, temperature? **Facilitator**: *She has much better color now and her peripheral pulses are much stronger. Her extremities are warmer*

Labs:

ISTAT 8 Na (135-145) MEQ/L: 140 K (3.6-5.1) MEQ/L:4.7 Cl (98-110) MEQ/L:100 CO2 (20-30) MEQ/L: 10 BUN (6-24) MG/DL: 32 Creat (0.4-1.3) MG/DL:0.3 iCa (1.1-1.3) Mmol/L: 1.10 Glu (67-109) MG/DL: 195 LACTATE8.0

DEBRIEFING SCRIPT QUESTIONS;

REACTIONS: to the general performance, this can include feelings or emotions and medical facts How did you feel about taking care of this child? How do you think the team did getting fluids into the patient? How do you think the team did in managing priorities in the care of this patient?

ANALYSIS: we will discuss the diagnosis management of the case based on the team's performance; this will include identifying gaps in performance and positives.

STEPS: observation + judgment+ inquiry

Ex: I noticed struggle in getting fluid in fast enough, tell me more about what you were thinking

What are some barriers to getting fluid in rapidly

During this time the group can ask questions of the facilitators.

SUMMARY: we review our discussion and findings. Each individual will summarize one thing that they learned from the

case and will apply in future care o

```
"Drill
```

Down" questions for use to follow up possible areas of interest What hindered/prevented you from ____? How did that (factor/distraction) affect your ability to ? What were you concerned about when ? Where did you learn how to ? What would have improved your ability to (make a decision/do a procedure/work with a teammate/handle a stressful or difficult situation)? How did you know that ? When did you realize/recognize that ? I saw that you (did this). What made you decide to (error of commission)? What made you decide not to (error of omission)? What else was going on at the time that made you (error of omission or commission)? What we re your priorities at the point in time when ? What were you thinking about when this happened? What were you planning to do when you saw that ? What prevented you from carrying out your plan? How much time did you think you had before you had to respond to ?

Data collection tools/measurements:

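### Bag-change training is not parallel across the three arms, which can bias timing against the pressure bag if a bag change occurs in the simulation

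*Protocol*

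**What the plan says.** The Protocol's Training section randomises participants first and trains them afterwards. Two elements are common to all arms: "A 5-minute training video is viewed on how to use the device that participants are randomized to", and a hands-on check in which "They will demonstrate ability to set up the device and fill an empty container with fluid".

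The device-specific lists then differ on bag changes:

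- **LifeFlow:** the cue "Participants reminded to change 1L bag when about 2cm fluid remain", followed by "Line is changed from first 1L bag to second and device continues to be used".
- **Push/pull:** the same practised change, with no cue about when to make it.
- **Pressure bag:** "1L bag placed in sleeve, spiked and tubing connected to IV", then "Sleeve pressurized to 300mmHg", where the list ends. It has neither the change nor the cue.

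The Set up section specifies "10 kg child with a 22-gauge IV catheter x 2, device and appropriate tubing", and the Trial section makes available an algorithm of three 20 cc/kg boluses. The secondary outcomes listed at the end of the Trial section give the requested volume as "60 ml/kg or 1200ml". Set-up, each bolus and the total for three boluses are timed, and rates are compared between boluses. The SAP sizes the study on a 3 ml/sec improvement in rate.

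**The concern.** Training is given after allocation, so it is part of what each arm receives, and any difference in it travels with the device. Moving from one bag to the next is needed in any arm that uses up a bag, and knowing when to do so is not presented as peculiar to LifeFlow. The fullest version of this training nevertheless goes to the study device and none of it to the pressure bag.

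If a team must change a bag while being timed, seconds lost to an unrehearsed change count in its bolus time and total time. They would then be read as a slower device. Push/pull teams rehearse the change but lack the cue, so any disadvantage to them should be smaller. There is also a risk of misinterpretation. A delay confined to the last bolus looks like slowing over successive boluses, and self-reported fatigue is itself a secondary outcome.

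**Working it through.** **Step 1. The plan's own volume.** Inputs: 10 kg (Set up); 20 cc/kg three times (Trial); 60 ml/kg or 1200 ml (secondary outcomes).

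- From weight and boluses: 10 × 20 × 3 = 600 ml.
- From the printed total: 1200 / 60 = 20 kg, which is not the stated weight.

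The 1200 ml cannot be reproduced from the 10 kg scenario, so the two passages conflict.

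**Step 2. Is a bag change needed?** Assume 1 L bags and one bag in use at a time. The 1 L size appears only under Training; the documents do not state the size used in the timed simulation.

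| Total volume | Cumulative volume after boluses 1, 2, 3 | Bags needed | Changes |
|---|---|---|---|
| 600 ml | 200, 400, 600 ml | 1 (400 ml left) | 0 |
| 1200 ml | 400, 800, 1200 ml | 2 | 1, in bolus 3 |

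The simulation also ends at 15 minutes. Emptying 1 L in that time needs an average of at least 1000 / 900 = 1.11 ml/s, and somewhat more once set-up time is deducted. Slower teams would not empty the first bag even if 1200 ml is the target.

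**Step 3. Size of the effect if a change occurs (1200 ml only).** The documents give neither a change time nor an expected rate. Assume that lack of practice adds d = 30 to 60 s, and take true rates r of 1.5 and 3 ml/s. Assume also that rate is volume over elapsed time, including the change. The apparent rate is V / (V/r + d), with V = 1200 ml overall and V = 400 ml for the third bolus.

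| True rate | Measure | d = 30 s | d = 60 s | Fall |
|---|---|---|---|---|
| 1.5 ml/s | Overall | 1200/(800+30) = 1.45 | 1200/(800+60) = 1.40 | 4-7% |
| 1.5 ml/s | Bolus 3 | 400/(266.7+30) = 1.35 | 400/(266.7+60) = 1.22 | 10-18% |
| 3 ml/s | Overall | 1200/(400+30) = 2.79 | 1200/(400+60) = 2.61 | 7-13% |
| 3 ml/s | Bolus 3 | 400/(133.3+30) = 2.45 | 400/(133.3+60) = 2.07 | 18-31% |

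**Step 4. Against the planned difference of 3 ml/s.** The overall loss is about 0.05-0.10 ml/s at 1.5 ml/s and 0.21-0.39 ml/s at 3 ml/s, or roughly 2-13% of the planned difference. The third-bolus loss is about 0.15-0.28 and 0.55-0.93 ml/s, or roughly 5-31% of it. Boluses 1 and 2 and set-up time are not directly affected.

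The 3 ml/s serves here only as a yardstick. The SAP gives no standard deviation, so its 8 teams per group cannot be reproduced, and nothing above depends on it.

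**The case against.** A reader might infer that the comparison is biased against the pressure bag, and that every team has to change a bag. The documents support neither. At the 600 ml that follows from the stated weight and boluses, one 1 L bag is enough and the direct effect is about zero. Only the conflicting 1200 ml forces a change, and then only for teams fast enough to reach it within 15 minutes. The Training section's two-bag exercise would fit a volume above 1 L, but it does not settle the conflict.

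Other points on that side also have weight:

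- The 30-60 s delay is an assumption, and the overall loss is small against 3 ml/s.
- Separate bolus timing, checked against video, would confine the effect to the third bolus and make it visible.
- Changing a bag inside a pressurised sleeve may take longer whatever the training. That extra time is a property of the device and should not be attributed to training.
- The pressure-bag list is terse; it omits priming as well. The content of the device video is not described and might cover bag changes. The gap could therefore lie in the description rather than in the training given.

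These arguments defeat an unconditional claim of bias. They do not justify the unequal lists. The Protocol treats the bag change as worth teaching in two of three arms. If it matters, the third arm needs it; if it does not, no arm does. Anyone following the lists as written would train the arms unequally.

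**Conclusion.** The asymmetry is plain on the face of the Training section. Its effect on the results is conditional: it can bias the timed comparison against the pressure bag, and slightly against push/pull, if a bag change takes place in the simulation. That requires 1200 ml and 1 L bags to apply, and a team quick enough to get there. Other routes to a change, such as smaller bags or overshooting past 1 L, are possible but not described.

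If the condition holds, and on the assumed delay and rates, the overall rate is understated by 4-13% and the third-bolus rate by 10-31%. The third-bolus comparison is the exposed one. If 600 ml from a 1 L bag applies, the direct effect is about nil. The plausible direction favours the study device and the remedy costs very little, so the change should be made under either volume.

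**What to change.** Reconcile the 10 kg, three-bolus scenario with the 1200 ml figure, and state the bag size used in the timed simulation.

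End all three training checklists in the same way: one practised change from the first to the second 1 L bag on the assigned device, and the same reminder about when to change. The cost is one bag and about 1-2 minutes in the pressure-bag arm, plus one added reminder line in the pressure-bag and push/pull lists.

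The SAP describes enrolment in the past tense, so sessions may already be complete. In that case:

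- state what training each arm actually received, including whether the video covered bag changes;
- report from the existing video whether and when bags were changed, by arm;
- show rates for boluses 1 and 2 separately from bolus 3;
- disclose the training difference as a limitation.

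The time a change takes on video mixes practice with the handling the sleeve itself requires. It should be reported as observed and not all ascribed to training. This costs a review of existing recordings and a few lines of reporting.

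### The target volume contradicts itself (600 ml from weight and bolus size, 1200 ml as printed), so volume accuracy and completion of three boluses are undefined; a minor gap follows for teams unfinished at 15 minutes.

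*Protocol*

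**What the plan says.** **Volume.** The protocol's Set up section specifies a 10 kg child. The Trial section makes available an algorithm of three 20 ml/kg boluses. Further down the Trial section, accuracy of delivery is a secondary outcome measured against the "requested volume (60 ml/kg or 1200ml" figure. In training, teams practise changing from one 1-litre bag to a second.

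**Timing.** The Trial section records: "Participants timed on setup, infusion of each bolus, total time for 3 boluses". It also asks the analyst to "Compare rate of fluid administration between first, second and third boluses".

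**Stop.** The Trial section says "Simulation ends after 15 min", and the case script repeats it: "CASE ENDS WITH SIGN OUT TO PICU @ 15 minutes from start". The vital signs follow the same clock, with a first trend over 5 minutes and then a "TREND OVER LAST 10 MINUTES". The introduction script says of the simulation "It ends when the moderator says" a closing phrase; this names who ends it but gives no other time. Phase 3 of the facilitator's answers opens "After third fluid bolus or vasoactive medications are initiated", so the script can move on without a third bolus.

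**Analysis.** The available SAP text sizes the study on a 3 ml/sec difference in rate, with nine teams in each of three groups. It names one-way ANOVA or Kruskal-Wallis and says parametric results are presented. It does not name total time and has no rule for a team unfinished at the stop. Part of the SAP was not available for this review.

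**The concern.** Volume accuracy needs one denominator, and the protocol prints two that differ by a factor of two. A complete delivery under one is half a delivery under the other, and a complete delivery under the other is a twofold excess under the first.

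The same figure decides when the third bolus is over, and so when the total-time clock stops. It also sets how demanding the 15-minute limit is. A team still infusing at 15 minutes gives only a lower bound for its total time. If such teams fall mainly in the slower arm, leaving them out makes that arm look faster than it is. An unfinished team in the faster arm can push the other way.

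**Working it through.** **1. The volume, from the protocol's own inputs**

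- Per kilogram: 20 ml/kg x 3 = 60 ml/kg. This reproduces the printed per-kilogram figure.
- At the stated weight: 60 ml/kg x 10 kg = 600 ml.
- Weight at which the printed total would hold: 1200 ml / 60 ml/kg = 20 kg.
- Size of one bolus: 20 x 10 = 200 ml, against 1200 / 3 = 400 ml.
- Accuracy score of a team giving 600 ml: 600/600 = 100%, or 600/1200 = 50%.

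The two-bag training step bears on the question without settling it. 600 ml is less than one 1-litre bag and 1200 ml is more than one, but the step is described as practice with the equipment.

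**2. Flow needed to finish by 15 minutes (900 s)**

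Minimum average flow = volume / (900 s - time lost). The documents give no time lost, so 0 to 300 s is assumed.

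| Time lost | 600 ml | 1200 ml |
|---|---|---|
| 0 s | 0.67 ml/s | 1.33 ml/s |
| 120 s | 0.77 ml/s | 1.54 ml/s |
| 300 s | 1.00 ml/s | 2.00 ml/s |

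The requirement doubles throughout.

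**3. What an unfinished team could do to total time (illustration only)**

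The documents give no times, device rates or SDs. Assumptions: 9 teams per arm; rates r, r + 1.5 and r + 3 ml/s, so that the outer arms differ by the SAP's 3 ml/s; total time normal, with mean = minutes lost + volume/(60 x rate) and SD 25% of the mean.

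With r = 2.0 ml/s and 5 minutes lost:

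- *600 ml.* Slow arm 5 + 600/120 = 10.0 min (SD 2.5); fast arm 5 + 600/300 = 7.0 min. The stop lies (15 - 10)/2.5 = 2 SD above the slow-arm mean, so about 2% of that arm is unfinished.
- *1200 ml.* Slow arm 5 + 1200/120 = 15.0 min (SD 3.75); fast arm 5 + 1200/300 = 9.0 min. The stop is at the slow-arm mean, so 50% of that arm is unfinished. The mean of finishers is 15 - 0.798 x 3.75 = 12.0 min. With unfinished teams entered as 15 minutes it is 15 - 0.399 x 3.75 = 13.5 min.

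| Slow minus fast, r = 2.0, 5 min lost | 600 ml | 1200 ml |
|---|---|---|
| Complete data | 3.0 min | 6.0 min |
| Unfinished dropped | 2.9 min | 3.0 min |
| Unfinished entered as 15 | 3.0 min | 4.5 min |
| Power, ANOVA, complete data | 74% | 95% |
| Power, ANOVA, dropped | 72% | 45% |
| Power, ANOVA, entered as 15 | 74% | 92% |
| Power, Kruskal-Wallis, unfinished tied worst | 69% | 92% |

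Power is from simulation (2,000 runs per case).

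**4. How far this depends on the assumptions**

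- 1200 ml, r = 2.0, 3 minutes lost: 27% of the slow arm unfinished.
- 1200 ml, r = 3, 5 minutes lost: 13% unfinished; a 3.3 min difference becomes 2.6 (dropped) or 3.1 (entered as 15).
- 1200 ml, r = 4, 5 minutes lost: 2% unfinished.
- 1200 ml, r = 3, 3 minutes lost: 1% unfinished.
- 600 ml, r = 3 or 4, 5 minutes lost: under 0.1% unfinished.

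**The case against.** On volume, one can say that the 1200 ml is a slip of the pen and that those running the sessions knew what was meant. One can add that accuracy is listed under the follow-up questionnaire and so may be a minor self-reported item. That may be so, but the documents do not show which figure is the slip. A reader might infer from the 10 kg weight that 600 ml was meant, or from the two-bag training that 1200 ml was meant; neither passage settles it. A questionnaire item on accuracy also needs a reference volume.

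On the 15-minute stop, most of the objection stands:

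- No passage shows an unfinished team. Teams rehearse set-up, find both IV lines in place and are prompted to continue fluids.
- Total time appears once, in a list of things timed. The available SAP text does not name it, and the part not seen could hold a rule.
- The large distortions need slow flow, 1200 ml and several lost minutes together. The inputs also fit poorly: if power 0.80 was meant (0.08 is printed), 8 teams per group implies a rate SD near 2 ml/s. A normal rate with mean 2.0 and SD 2 would be negative 16% of the time.
- The ninth team per group, added because of doubts about the study running per protocol, gives some cover for losing a team.

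A reader might also infer that ANOVA should give way to a rank test. The figures do not support that. Against ANOVA with unfinished teams entered as 15, Kruskal-Wallis gives 69% against 74% power and 92% against 92%. A restricted mean to 15 minutes is no way round either, because with one common stop it equals the mean with unfinished teams entered as 15. What does clear harm is dropping them, and no passage says that was done.

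**Conclusion.** The volume contradiction holds as plain arithmetic and needs no assumption. The stated weight and bolus scheme give 600 ml and the accuracy outcome prints 1200 ml, a factor of two. It is more than clerical, because the figure defines a stated outcome and what counts as three completed boluses.

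The unfinished-team point is minor and conditional. The stop at 15 minutes is clear and the available text has no rule for it, but whether it matters depends on the volume and on flow rates that the documents do not give. Under the assumptions above, the loss from dropping unfinished teams runs from 0.1 min in a 3.0 min difference (600 ml, 2.0 ml/s) to half of a 6.0 min difference (1200 ml, 2.0 ml/s). If all 27 teams finished, there is no bias.

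A reader might infer that the trial's main result is compromised. The documents do not support this. The study is powered on rate, and volume collected over infusion time can still be calculated for a partly given bolus. Only a bolus never started has no rate.

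**What to change.** 1. Reconcile the weight and bolus scheme with the printed total, taking the two-bag training step into account. State one volume, and use it both to score accuracy and to define completion of three boluses. This review does not say which figure is right.
2. Report, per arm, how many teams completed three boluses by 15 minutes. If all 27 did, say so and keep the ANOVA.
3. If any did not, keep them in the total-time comparison, either entered as 15 minutes or tied at the worst rank, and label the result accordingly. Do not drop them.

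The cost is a few lines of text. The clock, the video and the camera on the cylinder already supply the data, and both tests are already named in the SAP. The downside is that a mean with teams entered as 15 minutes still understates a slow arm's time (4.5 against 6.0 min for the difference in the worked 1200 ml case), hence the label. Ranking can cost about 5 points of power when few teams are unfinished (69% against 74%).

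### The accuracy outcome's 1200 mL target conflicts with the protocol's 10 kg patient, for whom 60 mL/kg is 600 mL

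*Protocol*

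**What the plan says.** The Protocol describes the patient and the dose in three places.

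- Set up gives the weight: "10 kg child with a 22-gauge IV catheter x 2, device and appropriate tubing".
- Trial gives the dose: "Algorithm available indicating 20cc/kg boluses x 3". It also sets what is timed: "Participants timed on setup, infusion of each bolus, total time for 3 boluses".
- The case lead-in gives the age: "EMS brought in a 1-year-old female patient with vomiting, fevers, tachycardia, and ill appearance".

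At the end of the Trial list, under a follow-up questionnaire on secondary outcomes, the Protocol names the participants' "ability to accurately administer the requested volume (60 ml/kg or 1200ml) to the simulated patient". The introduction script also expresses the dose per kilogram ("For example, if they want 20cc/kg bolus"). No weight other than 10 kg appears in the text available to this review.

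The available SAP text gives no target volume, no definition of accuracy and no analysis specific to it. Its sample size rests on a difference in rate of 3 mL/sec.

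**The concern.** The requested volume is the reference value for a named secondary outcome. It is given in two forms, per kilogram and in millilitres, and for the patient the protocol describes these differ by a factor of two. Someone who scores delivered volume from the protocol alone could defend either 600 mL or 1200 mL as the target. Any accuracy measure expressed relative to the target would then depend on which figure the scorer took.

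**Working it through.** **Inputs, all from the Protocol**

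- Weight: 10 kg (Set up).
- Dose: 20 mL/kg, three boluses (Trial).
- Stated target: 60 mL/kg, equated with 1200 mL (secondary outcomes at the end of Trial).

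**Step 1. Try to reproduce the stated target.**

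- Dose per kilogram: 20 x 3 = 60 mL/kg. This agrees with the first half of the parenthesis.
- Volume per bolus: 20 x 10 = 200 mL.
- Total: 3 x 200 = 600 mL. This does not agree with 1200 mL. The ratio is 1200 / 600 = 2.0.

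**Step 2. Ask what would make 1200 mL right.**

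| Reading | Arithmetic | Support in the text |
|---|---|---|
| Heavier patient | 1200 / 60 = 20 kg, so 400 mL per bolus | None; 10 kg is stated and the child is 1 year old |
| Higher dose at 10 kg | 1200 / 10 = 120 mL/kg | None; 60 mL/kg is stated |
| More boluses at 10 kg | 1200 / 200 = 6 boluses | None; three are specified and timed |
| Full dose through each of two IVs | 2 x 600 = 1200 mL, or 120 mL/kg in total | None; not prescribed anywhere |

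**Step 3. Sort the evidence by whether it separates the two figures.**

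- Fits either figure: the 20 mL/kg dose, the three timed boluses, and the facilitator responses that run to the third bolus. All are consistent with 60 mL/kg at any weight.
- Favours 600 mL: the stated 10 kg and the age of 1 year.
- Would fit a target above 1 L: the Training section has LifeFlow and Push/Pull participants change from a first 1 L bag to a second. On one line, 600 mL needs one bag, while 1200 mL exceeds one bag by 200 mL.

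**Step 4. Size of the effect, if accuracy is scored relative to target.** The visible text does not define the metric, so this step is conditional.

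- A team delivering exactly 600 mL scores 600 / 600 = 100% against one target and 600 / 1200 = 50% against the other.
- With a common target T, the between-arm difference in mean signed error is (m1 - T) - (m2 - T) = m1 - m2. T cancels, so differences in mean volume or mean signed error are the same under both targets.
- A between-arm difference in percent of target is 100 x (m1 - m2) / T, so doubling T halves it. For assumed arm means of 600 and 550 mL, it is 50 / 600 = 8.3 points or 50 / 1200 = 4.2 points.

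**The case against.** The strongest reply is that this is one parenthetical figure with the correct per-kilogram dose beside it. The algorithm made available to teams is per kilogram, so the millilitre figure need not have reached them at all. The outcome is secondary. Accuracy is listed under a questionnaire and may be self-reported, and although a graduated cylinder measures the fluid, no visible text ties it to this item. The bag-change step also leaves open that a target above 1 L was intended. All of this stands. It limits the size and direction of the point but does not remove the mismatch.

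A reader might infer more in three ways, none of which the documents support.

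- **That 1200 mL is certainly the wrong figure.** Only the weight and the age favour 600 mL, and the second bag points the other way. The bag change is weak evidence, because it belongs to training with an empty container, states no weight or target, and is not listed for the pressure bag. It is still enough to rule out certainty.
- **That results were mis-scored or teams ranked wrongly.** Under absolute error against 1200 mL, an assumed delivery of 700 mL (error 500) would beat an exact 600 mL (error 600). But the visible text defines no such metric. Nothing is shown under the Protocol's closing heading on data collection tools, and part of the SAP was not available to this review.
- **That teams were pushed toward 1200 mL.** The Protocol says "Participants prompted if necessary to continue giving fluids", with no volume attached, and nothing suggests that this happened.

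**Conclusion.** The conflict is real and rests on plain arithmetic: at the stated 10 kg, 60 mL/kg is 600 mL, and the written 1200 mL is twice that. The more likely correction is to 600 mL, on the strength of the stated weight and the child's age, but the documents do not settle it.

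The consequence is confined to a secondary outcome and is conditional on scoring relative to target, where an exact 10 kg dose would read as 50% instead of 100%. Comparisons of mean delivered volume between arms do not change. The SAP's 3 mL/sec difference and its 8 teams per group do not depend on this number. This is a minor fix, but more than a typing slip, because the figure is the outcome's reference value.

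**What to change.** In the secondary outcome, replace 1200 mL with 600 mL (200 mL per bolus) for the 10 kg patient, and use that as the only target for accuracy. If 1200 mL was intended, change the patient's weight to 20 kg (400 mL per bolus) and make the age in the case script fit.

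The first option costs one number. If accuracy was taken from delivered volume and compared with 1200 mL, it can be recalculated without new data, since the Protocol has "Cameras set up on graduated cylinder and overall resuscitation". That assumes the teams were working to the 10 kg dose. The second option costs edits to the weight and the case script.
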